4.3. Primary Endpoint Analysis

The primary efficacy assessment, guided by the “efficacy estimand”, will be conducted using the EAS. For the “efficacy estimand”, the hypothetical strategy is used to handle the ICE (permanent discontinuation of study drug), so only data collected before the occurrence of any such ICEs will be used in the MMRM estimation (Section 4.1). Through the MMRM, the potential efficacy measures (after the ICEs) had participants not experienced ICEs will be implicitly imputed. To confirm efficacy of LY3437943 with adequate statistical power, the evaluation of the efficacy and safety endpoints for LY 4.0 mg and LY 8.0 mg compared with placebo will be made by pooling 2 dose escalation regimens, ie, combine LY 4.0 mg (2.0 mg) and LY 4.0 mg (4.0 mg) as LY 4.0 mg (pooled), and combine LY 8.0 mg (2.0 mg) and LY 8.0 mg (4.0 mg) as LY 8.0 mg (pooled). The primary efficacy comparison will be based on the contrast between each treatment group of LY3437943 and placebo at Week 24 (Visit 13) from the MMRM analysis of percent change from baseline in body weight using the EAS (Section 4.1). The analysis model and selection of covariance structure is described in Section 4.1. Treatment comparisons will be performed for the primary objective at the full significance level of 0.05.

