Dose escalation will occur in certain treatment groups up to Week 12 of treatment. On Visit 6 through Visit 8, study participants are required to report after approximately 8 hours without eating, drinking (except water), or performing any significant physical activity. The mental health questionnaires (PHQ-9, C-SSRS, and Self-Harm Form) should be completed after the assessment for AEs during visits as indicated in the SoA, Section 1.3. For maintenance doses equal to or greater than 4 mg, the initial dose will be 2 or 4 mg followed by additional escalation steps as appropriate and described below. The dose will be increased at 4-week increments until the maintenance dose is achieved (Section 6.1 for details), as follows:

- Maintenance dose of 1 mg: no dose escalation
- Maintenance dose of 4 mg will be randomized 1:1 into 2 subgroups:
 - Subgroup (a): 2 mg (Visit 4) → 4 mg (Visit 6)
 - Subgroup (b): 4 mg (no dose escalation)
- Maintenance dose of 8 mg will be randomized 1:1 into 2 subgroups:
 - Subgroup (a): 2 mg (Visit 4) → 4 mg (Visit 6) → 8 mg (Visit 7)
 - Subgroup (b): 4 mg (Visit 4) → 8 mg (Visit 6)
- Maintenance dose of 12 mg:
 - 2 mg (Visit 4) → 4 mg (Visit 6) → 8 mg (Visit 7) → 12 mg (Visit 8).

Maintenance dose will be continued for the remainder of the study. Study site personnel will review the study drug preparation and injection technique using a vial and syringe at each visit. Refer to Section 6.5.1 and 6.6 for guidance on management of participants who experience GI symptoms.

Maintenance Period (Visits 9-17)

During the maintenance period, visits will occur monthly through 48 weeks. Telephone visits will occur at Weeks 28, 32, 40, and 44. For office visits, study participants are required to report after approximately 8 hours without eating, drinking (except water), or performing any significant physical activity. Office and telephone visit procedures should be conducted according to the SoA (Section 1.3). At Visit 11 and Visit 17, when collected, patient-reported outcomes questionnaires should be administered as early as possible in the visit. Preferred administration order is

1. Patient Global Impression of Status for Physical Activity
2. SF-36v2 acute form, and
3. Eating Inventory.

The mental health questionnaires (PHQ-9, C-SSRS, and Self-Harm Form) should be completed after the assessment for AEs during visits as indicated in the SoA, Section 1.3.

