ABPM will be repeated at Week 24 (Visit 11) and Week 36 (Visit 14) as described in Section 4.1.2.3. Study drug and injection supplies will be returned per the SoA (Section 1.3) and according to local requirements. New supplies will be dispensed as needed. Study site personnel will review the study drug preparation and injection technique using a vial and syringe at each office visit. Participants should be instructed to contact the investigative site for assistance as soon as possible if they experience any difficulties administering their study drug. Additional unscheduled visits may be scheduled if the participant needs additional support for the study drug injection technique.

Participants should also be advised about the appropriate course of action if study drug is not taken at the required time (for details on late/missing doses, see Sections 6.1 and 6.6). Study participants will be permitted to use concomitant medications that they require during the study, except certain excluded medications (see Section 6.5) that may interfere with the assessment of efficacy and safety characteristics of the study treatments.

Early Discontinuation of Treatment Visit

Participants unable or unwilling to continue the study treatment for any reason will perform an early discontinuation of treatment (ED) visit. If the participant is discontinuing during an unscheduled visit or a scheduled visit, that visit should be performed as an ED visit. A study participant who discontinues study drug permanently should be encouraged to continue in the study and to complete all study visits, including Visit 801 (See Participant Disposition and Timing of Safety Follow-Up figure below). Procedures should be completed according to the SoA (Section 1.3). When collected, patient-reported outcomes questionnaires should be administered as early as possible in the visit. Preferred administration order is

1. Patient Global Impression of Status for Physical Activity
2. SF-36v2 acute form, and
3. Eating Inventory.

Mental health questionnaires (PHQ-9, C-SSRS, and Self-Harm Form) should be completed after the assessment for AEs.

Visit 99

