4.1.2.3. ABPM

The ABPM device will be attached to the nondominant arm and participants will be instructed to wear the monitor for a 24- to 27-hour period. Participants will be instructed to keep track of daily activities throughout the testing period and not to engage in strenuous activity.

Ambulatory BP measurements

- should be collected on a typical workday, not on a non-working day
- will be recorded every 30 minutes during daytime hours (0700 to 2200 hours), and
- will be recorded every 60 minutes during nighttime hours (2200 to 0700 hours).

A 24-hour session of ambulatory monitoring produces technically acceptable measurements if $\geq 70\%$ of the readings are valid. Between Visit 3 and Visit 4 (Week 0) and within 7 days following Visit 11 (Week 24) and Visit 14 (Week 36), participants will undergo a 24-hour ambulatory monitoring session. Upon return of the ABPM device, the recordings must be transmitted to the Core Laboratory and reviewed for validity of the readings before the participant leaves the site. If a technically satisfactory result is not achieved (less than 70% of readings are valid), the investigator should review the device settings and placement and the participant's activity track to correct any user error or device malfunctions. Another 24-hour ambulatory monitoring session should be conducted prior to Visit 4 (Randomization) or within 14 days following Visit 11 and Visit 14, respectively. If the second session also provides technically unsatisfactory results, data will be considered missing and the participant may continue in the study.

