Treatment effect of interest is thus defined as the difference in mean percent changes in body weight at Week 24 between QW LY3437943 and placebo.

Rationale for “efficacy estimand”: This Phase 2 study aims to study the efficacy of LY3437943 under the ideal condition that all participants adhere to the randomized treatment.

Estimand(s) for Secondary Objectives

The same estimand for the primary objective will be used for the following efficacy endpoints for the secondary objectives:

- difference between LY3437943 and placebo in percent change from baseline in body weight at Week 48
- percentage of participants with 5% or higher, 10% or higher, and 15% or higher body weight loss from baseline at Weeks 24 and 48
- change from baseline in body weight (kg) at Weeks 24 and 48
- change from baseline in BMI (kg/m²) at Weeks 24 and 48; and
- change from baseline in waist circumference (cm) at Weeks 24 and 48.

Unless specified otherwise, safety and tolerability assessments will be guided by an estimand comparing safety of LY3437943 doses with placebo for the whole study period (the treatment period plus safety follow-up period) irrespective of adherence to study intervention for all study population (including inadvertent enrollment).

Supplemental Estimand(s) for Primary Efficacy Endpoint

An alternative estimand, called “hybrid estimand”, is the mean treatment difference in percent change in body weight from baseline at Week 24 between LY3437943 and placebo in participants who meet the inclusion criteria with ICEs handled differently according to the reasons for the events:

- Category 1: The ICEs of permanent discontinuation of study drug due to reasons unlikely related to the efficacy/safety outcomes will be handled by the hypothetical strategy.
- Category 2: The ICEs of permanent discontinuation of study drug due to lack of efficacy before study treatment discontinuation will be handled by the hypothetical strategy
- Category 3: All other ICEs will be handled by the treatment policy strategy. With treatment policy strategy, the occurrences of “permanent discontinuation of study drug” is considered irrelevant in defining the treatment effect of interest. The value for the response variable is used regardless of whether or not the ICE occurs.

Population-level summary: mean percent change in body weight at Week 24.

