4.3.1. Definition of Endpoint

The primary efficacy measure will be percent change in body weight from baseline (Week 0) to Week 24. The percent change in body weight at each nominal visit is defined as:

$$\frac{(\text{post baseline body weight [kg]} - \text{baseline body weight [kg]})}{\text{baseline body weight [kg]}} * 100\%.$$

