7.4. Appendix 4: Treatment Compliance

Listing and summary of prematurely discontinuing study treatment (including discontinuation reason) and discontinuing study will be provided by treatment groups and dose escalation subgroups. Kaplan-Meier plots of time to premature study treatment discontinuation and time to

premature study treatment discontinuation due to AE will be provided at Weeks 24 and 48 based on all randomized population. Kaplan-Meier plots of time to premature study discontinuation will be provided at Weeks 24 and 48 based on all randomized population. Time-to-event analyses of premature study treatment discontinuation, study treatment discontinuation due to AE, and study discontinuation may be conducted at Weeks 24 and 48.

If data warrants, the counts and percentages of participants who follow the planned dose escalation scheme, have dose interruption, or have dose de-escalation will be summarized for each treatment group and dose escalation subgroups. Listing of overdose of LY3437943 and placebo will be provided.

Per protocol, treatment compliance will be assessed every 4 weeks, or every 12 weeks after Visit 11, at the time of visits to the study site. Treatment compliance will be defined as taking at least 75% of the scheduled LY3437943 or placebo doses. Compliance at each treatment compliance assessment visit mentioned above and over the corresponding study period will be calculated using the number of doses administered (regardless of the actual dose in unit or mL administered) divided by the total number of doses expected to be administered $\times 100$ at the specific visit or over the corresponding study period, respectively. Treatment compliance will be summarized descriptively at each treatment compliance assessment visit and over the corresponding study period by treatment groups and dose escalation subgroups using the full analysis set.

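### Does the visit number in SAP 4.3 (Visit 13) put the primary contrast at the wrong time point?

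*SAP*

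**What the plan says.** SAP 4.3 defines the primary comparison by a week and, in brackets, a visit number: "The primary efficacy comparison will be based on the contrast between each treatment group of LY3437943 and placebo at Week 24 (Visit 13".

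The sections around it give only the week. SAP 4.3.1: "The primary efficacy measure will be percent change in body weight from baseline (Week 0) to Week 24". The primary estimand in SAP 1.1 targets "the difference in mean percent changes in body weight at Week 24 between QW LY3437943 and placebo".

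The protocol attaches Week 24 to a different visit number. Section 4.1.1.1: "ABPM will be repeated at Week 24 (Visit 11) and Week 36 (Visit 14". Section 4.1.2.3 places the same monitoring sessions "within 7 days following Visit 11 (Week 24) and Visit 14 (Week 36". On the contacts after Week 24, Section 4.1.1.1 says: "Telephone visits will occur at Weeks 28, 32, 40, and 44".

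**The concern.** The sentence in SAP 4.3 specifies the one comparison on which the trial's primary claim rests, and it carries two identifiers that disagree. The visit number could matter in practice. SAP 4.1 fits a repeated-measures model whose effects are estimated separately at each visit, and SAP 4.3.1 computes percent change visit by visit. A programmer could therefore reasonably key the contrast to a visit number instead of a week.

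If the bracketed number governed, the primary analysis would be aimed at Week 32, eight weeks after the intended time point, at a telephone contact where weight is not measured. A reader comparing the SAP with the protocol might also ask whether the primary time point had been moved.

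**Working it through.** No statistical calculation decides this point. The check is to line up the schedule and see what each identifier leads to.

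**1. Visit-to-week map.** The protocol's Schedule of Activities (Section 1.3), with the visit row read against the week, telephone and weight rows, gives:

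| Visit | Week | Contact | Weight scheduled |
|---|---|---|---|
| 4 | 0 | clinic | yes (baseline) |
| 5, 6, 7, 8, 9, 10 | 1, 4, 8, 12, 16, 20 | clinic | yes |
| 11 | 24 | clinic | yes |
| 12 | 28 | telephone | no |
| 13 | 32 | telephone | no |
| 14 | 36 | clinic | yes |
| 15, 16 | 40, 44 | telephone | no |
| 17 | 48 | clinic | yes |

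The scheduled post-baseline weights in the treatment period fall at Visits 5 to 11 (7 visits) plus Visits 14 and 17, so 7 + 2 = 9. Visit 11 is one of the nine and Visit 13 is not. Protocol 8.1 confirms that weight is taken at clinic visits.

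**2. Is the map an artefact of a broken table?** No. Running text in protocol Sections 4.1.1.1 and 4.1.2.3 gives Visit 11 as Week 24 and Visit 14 as Week 36. That leaves two monthly contacts between them, Weeks 28 and 32, as Visits 12 and 13. Both are on the protocol's list of telephone weeks.

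**3. Is it a change of protocol version?** Nothing suggests so. The SAP says it rests on the protocol of 21 May 2021. The change log for that amendment already places the maintenance-period questionnaires at Visits 11 and 17, and no renumbering of visits appears among the listed changes. SAP Appendix 4 (Section 7.4) is also consistent with the map: "treatment compliance will be assessed every 4 weeks, or every 12 weeks after Visit 11". Twelve-week steps from Week 24 land on Weeks 36 and 48, which are the clinic Visits 14 and 17. That passage gives no week for Visit 11, so it supports the map without proving it.

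**4. Which identifier is intended?** Week 24 is the stated primary time point in SAP 1.1, 1.2, 2, 4.3.1 and 5, and in protocol 9.1, 9.2 and 9.4.3. Two operational provisions agree. Protocol 9.5 allows the primary database lock once everyone has completed 24 weeks, when the last participants would not yet have reached Week 32. Appendix 12 of the protocol gives its widest visit window, up to 28 days late, to Visits 11, 17 and 99. These are the Week 24 and Week 48 measurements, and Visit 13 is not among them.

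**5. What would a literal reading produce?** SAP 4.1 puts observations from scheduled post-baseline visits into the model. With no weight scheduled at Visit 13, there is no planned Visit 13 mean to contrast. The documents do not say whether programs are keyed by week or by visit number. The likely outcome of keying to Visit 13 is a missing or non-estimable result that someone would notice, not a plausible wrong number.

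**6. The plan's own figure.** Power uses 300 × 2/10 = 60 randomised per dose group and 60 × 0.8 = 48 completers, with a difference of 8 and an SD of 10. The noncentrality is 8 / (10 × √(2/48)) = 3.92 on 94 degrees of freedom. With two-sided alpha 0.05 the power is 97.2%, which reproduces the stated figure of at least 97%. No input is a visit number, so the label cannot affect it.

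**The case for a change.** The best case for a change is that this is the operative sentence for the primary contrast, that the model and the endpoint are organised by visit, and that SAP 4.8 requires the interim analyses to follow the same methods, so the text is relied on more than once. A plan should not leave its reader to decide which half of a bracketed pair governs, and replacing one number costs nothing.

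Part of this stands. The label is wrong, and neither the table extraction nor a protocol version explains it. What does not follow is any consequence. For the slip to matter, someone would have to prefer the bracketed number over the week printed beside it, disregard the endpoint definition in the next subsection, and then obtain a result from a telephone contact with no planned weights. The interim analyses add nothing: each would use the same schedule, in which weights exist at Visit 11 and not at Visit 13. That a correction is free does not show that it gains anything.

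**Conclusion.** This is a clerical slip and no change to the plan follows. One visit number in SAP 4.3 should read 11 and reads 13. Week 24 is fixed unambiguously by the same sentence, by the endpoint definition and estimand, and by the protocol's hypotheses, sample size and primary-analysis sections. Correcting the label would leave the data collected, the endpoint, the estimand, the model, the significance level, the power (97.2% on the plan's assumptions) and the treatment estimate as they are. It would alter neither what the trial does nor what it can conclude.

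This rests on two assumptions. The first is that the Schedule of Activities has been read correctly, which the protocol's running text confirms for Visits 11 and 14 and for the telephone weeks. The second is that a contrast keyed to a visit without scheduled weights would be noticed before reporting. That is very likely, though the documents do not describe the programming.

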4.3.1. Definition of Endpoint

The primary efficacy measure will be percent change in body weight from baseline (Week 0) to Week 24. The percent change in body weight at each nominal visit is defined as:

$$\frac{(\text{post baseline body weight [kg]} - \text{baseline body weight [kg]})}{\text{baseline body weight [kg]}} * 100\%.$$

4.3.2. Main Analytical Approach

Percent change from baseline in body weight will be analyzed using the MMRM model for the “efficacy estimand” as described in Section 4.1.

4.3.3. Analyses for Supplemental Estimand(s)

The analysis related to a supplemental estimand, “hybrid estimand” (Section 1.1), will be conducted using data in the randomized population.

Hybrid estimand is defined as the treatment difference in the mean percent change in body weight from baseline at Week 24 between LY3437943 and placebo for the study target population with ICEs handled differently according to the reasons of the events as follows:

- Category 1: The ICEs of permanent discontinuation of study drug due to reasons unlikely related to the efficacy/safety outcomes will be handled by the hypothetical strategy.
- Category 2: The ICEs of permanent discontinuation of study drug due to lack of efficacy before study treatment discontinuation will be handled by the hypothetical strategy.
- Category 3: All other ICEs will be handled by the treatment policy strategy.

In this study, following ICH E9 (R1) guidance, a plan was made to collect informative treatment disposition reasons, through eCRF, for why data intended for collection are missing and classify them into categories 1 through 3 as shown in [Table GZBF.4.1](#) (ICH 2019).

Table GZBF.4.1. Treatment Disposition Reasons

Disposition Reason	Associated Sub-Categories	Category
Adverse event		3
Protocol deviation	Due to epidemic/pandemic	1
	Other	3
Pregnancy		3
Lack of efficacy		2
Other		3
Withdrawal by subject	Concern about study procedures/perceived risks	3
	Scheduling conflicts	1
	Subject is moving or has moved	1
	Personal issue unrelated to trial	1
	Due to epidemic/pandemic	1
	Other (option to include a specify field)	3
Physician decision	Concern about study procedures/perceived risks	3
	Scheduling conflicts	1
	Subject is moving or has moved	1
	Due to epidemic/pandemic	1
	Other (option to include a specify field)	3
Study terminated by sponsor		1
Site terminated by sponsor		1
Study terminated by IRB/ERB		1

Abbreviations: ERB = ethical review board; IRB = institutional review board.

To estimate the “hybrid estimand,” multiple imputation will be used to impute the corresponding missing potential outcome according to the missingness patterns (Table GZBF.4.2) with ICEs handled differently according to the reasons of the events.

When participants have missing values without ICEs, the missing values will be imputed using data from participants who do not have ICE or missing values.

Percent change from baseline in body weight will then be analyzed using ANHECOVA with terms of treatment group: placebo, LY 1.0 mg, LY 4.0 mg (2.0 mg), LY 4.0 mg (4.0 mg), LY 8.0 mg (2.0 mg), LY 8.0 mg (4.0 mg) and LY 12.0 mg (2.0 mg), stratification factors including gender (female, male) and baseline BMI stratum (less than 36, greater than or equal to 36), and continuous covariate of baseline value, along with the interaction between treatment group and the stratification factors and that between treatment group and the baseline value. The heteroscedasticity is also considered by introducing treatment specific variance estimates. This formulation has been shown to provide the optimal efficiency gain regardless of randomization schemes within the class of linear model adjustment (Ye et al. 2009).

The evaluation for LY 4.0 mg and LY 8.0 mg compared with placebo will be made by pooling 2 dose escalation regimens, ie, combine LY 4.0 mg (2.0 mg) and LY 4.0 mg (4.0 mg) as

LY 4.0 mg (pooled), and combine LY 8.0 mg (2.0 mg) and LY 8.0 mg (4.0 mg) as LY 8.0 mg (pooled).

Table GZBF.4.2. Strategy to Handle ICE and Missingness for Hybrid Estimand

ICE	Strategy to Handle ICE	Assumptions for Missingness	Methods to Handle Missing Values at Endpoint
Category 1: Treatment discontinuation due to reasons unlikely related to efficacy/safety outcome	Hypothetical	MAR	Data collected after the ICE will be set to missing. Missing values will be imputed using all nonmissing data (excluding data collected after ICEs) from the same treatment arm.
Category 2: Treatment discontinuation due to lack of efficacy	Hypothetical	MAR	Data collected after the ICE will be set to missing. Missing values will be imputed using all nonmissing data (excluding data collected after ICEs) from the same treatment arm.
Category 3: All other treatment discontinuations	Treatment policy	MNAR Considers that these participants could not adhere to their assigned treatment and may not benefit from the assigned treatment.	Missing values will be imputed using participants in the same treatment arm with similar ICEs but nonmissing values (retrieved dropout imputation). In cases where there are not enough retrieved dropouts to provide a reliable imputation model, will impute the missing data using the jump-to-reference (placebo) imputation approach. For Study GZBF, the likelihood of sufficient retrieved dropouts is assumed low.

Abbreviations: ICE = intercurrent event; MAR = missing at random; MNAR = missing not at random.

A sensitivity analysis may be conducted related to an alternative version of a hybrid estimand with the details provided below. The purpose of such a sensitivity analysis is to explore the best definition and handling strategy for the hybrid estimand in support of the compound development for chronic weight management. The difference from the aforementioned hybrid estimand mainly lies in the strategy to handle ICEs:

- Category 1: The ICEs of permanent discontinuation of study treatment due to reasons unlikely related to the efficacy/safety outcomes (i.e., personal reasons, scheduling conflicts, relocation, pandemic, geographic conflicts, etc.) will be handled by the hypothetical strategy. Generally, these ICEs will also cause participants to discontinue from the study. The potential outcome of the response if participants would continue the study treatment will be of interest. This is of best clinical interest as in real life — either these ICEs do not prevent participants from taking the medication or these ICEs (pandemic or geographic conflicts) do not represent the situation at normal time.
- Category 2: The ICEs of permanent discontinuation of study treatment due to adverse events or lack of efficacy will be handled by the treatment policy strategy. The potential outcome is the response after stopping taking the study treatment from the time of treatment discontinuation without the use of other anti-obesity medications.

- Category 3: The ICEs of the use of anti-obesity medication post permanent treatment discontinuation will be handled by hypothetical strategy. The potential outcome of the response without using the anti-obesity medication will be the interest.
- Category 4: All other ICEs, i.e., the ICEs of permanent discontinuation of study treatment due to all other reasons, will be handled by the treatment policy strategy. The potential outcome is the response after stopping taking the study treatment from the time of treatment discontinuation without the use of other anti-obesity medications.

The strategies for imputing missing data for different categories of ICEs are as follows, in line with the corresponding strategies.

- Category 1: data collected after these ICEs are excluded. The resulting missing values can be imputed using those participants who adhere to the study medication in the same treatment group under the assumption of Missing At Random (MAR).
- Categories 2 and 4: data collected after these intercurrent events will be used. Additional missing values will be imputed by using the observations for those who discontinue study treatment due to these corresponding ICEs and who have data collected post these ICEs (retrieved dropout approach) or by jump to reference (placebo imputation) under the assumption of Missing Not At Random (MNAR).
- Category 3: data after initiation of the ICEs will be excluded. Since anti-obesity medication other than LY3437943 is prohibited until the participants discontinue the study treatment, we assume that the ICEs of such treatment discontinuation associated with the use of anti-obesity medication belong to the Categories 2 or 4, e.g., study treatment discontinuation due to lack of efficacy. The resulting missing values will be imputed using the strategies as defined in Category 2 and 4.

The alternative methods of handling ICEs and imputing missing values are summarized in [Table GZBF.4.3](#).

Table GZBF.4.3. Strategy to Handle ICE and Missingness for Hybrid Estimand

Type of ICE	Strategy to handle ICE	Potential outcome	Handling data after ICE	Missing data imputation
Category 1	Hypothetical	The outcome if participants would adhere to the study medication	To discard	Imputing using the observed data up to ICEs from the same treatment group, based on the MAR assumption
Category 2	Treatment policy	The outcome as the result of ICE	To use	Imputing using retrieved dropouts or placebo arm,
Category 3	Hypothetical	The outcome if participants would not	To discard	

Type of ICE	Strategy to handle ICE	Potential outcome	Handling data after ICE	Missing data imputation
		take anti-obesity medication		based on MNAR assumption
Category 4	Treatment policy	The outcome as the result of ICE	To use	

Abbreviations: ICE = intercurrent event; MAR = missing at random; MNAR = missing not at random.

The analysis related to “adherer estimand” will be conducted using data in the EAS. “Adherer estimand” is the treatment difference in percent change in body weight from baseline at Week 24 between LY3437943 and placebo in participants who would adhere to both LY3437943 and placebo. We define that a participant adheres to the treatment if he/she has taken at least 75% of the study drug without permanent study drug discontinuation. A multiple imputation approach proposed by Luo et al. (2021) will be used. The data used for the imputation may include the baseline covariates, intermediate outcomes/variables, adherence status and the final outcome of percent change in body weight from baseline at Week 24. Such data for each treatment group is used to impute the potential outcomes (including intermediate and final outcomes, and adherence status) for participants assigned to other treatment groups.

After imputation, for each participant the potential outcomes for the final outcome of percent change in body weight from baseline at Week 24 and adherence status under all the treatments are available. Then, the mean response for each treatment group can be estimated by simply taking the average of the potential final outcomes for the adherers. The estimation of the treatment difference for the “adherer estimand” can be subsequently derived by taking the difference between the calculated mean responses. The inference is provided based on variance estimated by bootstrap.

